### **Quality control of intervention delivery**

Delivery of 3 exercise programs at multiple sites introduces the potential for inconsistent delivery of study programs. We have taken the following steps to improve quality control over intervention delivery: 1) Exercise instructor training sessions for all instructors. A 2-day training workshop, led by [name], [name], and the Project Director or the head exercise trainer, will cover how to instruct each exercise protocol, training progression, safety considerations, and research conduct specific to the exercise program. 2) Written guidelines will be provided for each instructor, in addition to hands-on training, that outlines the training protocols and overall study conduct to optimize delivery of the classes in a consistent fashion, 3) Rigorous oversight of class instruction. A primary role of the Project Director or the head exercise trainer will be to oversee proper conduct of exercise classes, participant retention and exercise compliance. She will observe classes on a weekly basis over the first 3 months and monthly thereafter. She or the head exercise trainer will work with instructors to minimize instructional differences across sites. Using this approach in our current fall prevention trial we have trained 7 instructors to deliver 15 study programs and have no differences across instructors on participant adherence or retention.

### **Participant safety during exercise**

Any form of exercise carries a slight risk of injury. We have had no drop out from a study due to injury during training; however, as with any study in older adults, compliance has been affected by minor musculoskeletal complaints usually stemming from pre-existing orthopedic conditions. We take steps to reduce the risk of injury and other issues that might limit compliance, including: 1) required physician clearance for every enrolled participant and 2) monitoring and early care of musculoskeletal symptoms which may include slight adjustments in the training program (modifying intensity or select exercises) with a goal to maintain the overall training stimulus.

### **Six-Month Follow-Up Period**

To evaluate the persistent effects of tai ji quan and strength training on falls and frailty, men will be followed for an additional 6 months after the 6-month supervised intervention stops. Men will continue to track their falls during the follow-up period using the same monthly reports employed in the intervention phase. A quarterly falls questionnaire will also be administered (3-months, 6-months, 9-months, and 12-months). We recognize that men may wish to maintain their exercise habits after formal training stops and we will not discourage them from doing so. During the follow-up period, exercise questionnaires will be used to track participation in home or community exercise programs and will be collected at the 9- and 12-month time periods. We will consider participation in community and/or home-based exercise in analysis for Aim 3 (see **Analysis Plan**) and will also repeat measures of frailty and function in order to better assess both the residual effects of the intervention programs among men who do not exercise in the follow-up period and the influence of continued exercise on outcomes after formal training stops.

**Participant Incentives:** To improve motivation to exercise and promote compliance to the study interventions, an incentive will be provided to participants at the mid-point and end of the intervention period. Participants will be provided with a potential to earn \$50 at each 3-month time point (\$100 for 6-month intervention) depending on their attendance at weekly exercise sessions. The amount received will depend on the average number of exercise class sessions attended per week. We will use the following compensation structure:

# of classes attended/12 week increment	average # of classes/week	Compensation amount
25-36	2.1-3.0	\$50.00
13-24	1.1-2.0	\$40.00
7-12	0.51-1.0	\$30.00
0-6	0.0-0.50	\$0.00

In addition there will be a \$15 remuneration per in-person testing visit to offset transportation costs. There will be an additional \$10 for completion of remote testing visits and \$10 for the completion of surveys at each of the four main time points. Participants who complete both in-person and remote testing and complete surveys at each of the four time points will be given a maximum amount of remuneration of \$140 (\$35 per time point). If a participant's travel exceeds a 60-mile roundtrip, they will receive an additional \$25 remuneration plus added compensation for excess miles driven (outside of the 60-mile roundtrip) using the 2020 standard mileage rate for medical visits of 17 cents per mile. This compensation will not exceed \$50 per testing time point for a maximum total compensation of \$200 per participant for travel. When travel exceeds 150 miles roundtrip, they may be provided with one night of hotel accommodations in the OHSU vicinity.

## Measures and Data Collection

Data on falls will be collected monthly while other measures will be collected at enrollment, 3- and 6-mos. (post-intervention), and 6 mos. after completion of the intervention (follow-up). A mid-study time point is included to detect early changes in frailty and function. Total time for performance testing and survey completion is ~2-2.5 hours. Men complete written surveys on a desktop or laptop computer at baseline and online for follow-up visits, unless they prefer to complete paper surveys (~5% of participants in our last intervention trial prefer paper over online). Staff reviews surveys for completeness and follows up with participants in person or by phone on missing data.

## Outcome Measures

### Primary Endpoint: Falls

In this study, a fall is defined as unintentionally coming to rest on the ground or at some other lower level, not as a result of a major intrinsic event (e.g., stroke or syncope) or overwhelming hazard [13]. Falls over one year prior to baseline will be ascertained to characterize the sample and check for equality of randomization. Prospective assessment of falls will be done using the current gold standard of collecting monthly reports [45] returned by postal and/or electronic mail, an efficient (1-2 minute completion time) and effective method used by our team and others [41, 46-48]. In two prior studies we obtained 98% of monthly fall reports over 6 months [46, 49]. Participants will be provided with a monthly falls calendar to record falls when they occur, in order to reduce issues of recall and false negatives. Each participant that records a fall will be phoned to confirm that each fall meets the standard definition in order to reduce the risk of false positives, and to obtain information about the fall (e.g., how it occurred) and any resultant injury. An “injurious” fall is one that results in fractures, head injuries, sprains, bruises, scrapes, or serious joint injuries, or where the participant seeks medical care [13]. Of primary interest in the proposed study is the # of falls, with the # of injurious falls and medical care resulting from a fall being used for descriptive purposes of the study population.

Secondary Endpoint: Frailty will be measured using the components of the Frailty Phenotype [29]. The original 5 criteria of the phenotype (shrinking, exhaustion, low activity, slowness, and weakness) were limited to the measures available in the Cardiovascular Health Study [29]. The phenotype can now be measured more accurately with objective measures (e.g., lean body mass rather than self-report weight loss[50]). In this study, we will assess each frailty component using measures that will most accurately capture frailty criteria in the prostate cancer survivor population and where cutoff scores can be appropriately determined. A total frailty score will be calculated in the same manner as that of Fried:  $\geq 3$  criteria = frail; 1-2 criteria = prefrail; 0 criteria = robust. Since each variable is a continuous measure we will examine changes in each individual frailty component to determine how each intervention may shift frailty among our sample. Criteria are measured as follows:

1. *Shrinking*: Since weight gain is a common side effect of ADT capturing the loss of lean mass that the “shrinking” component of the Frailty Phenotype was intended to capture may be difficult by tracking weight loss alone. Rather, we will measure lean mass by whole body by DXA (Hologic-QDR Discovery Wi; APEX software, v.4.02) scan performed by trained research personnel. The CV for body composition measures in our lab is  $<1.0\%$ . We will also measure lean mass by bioelectric impedance analysis (BIA; Imp SFB7, ImpediMed, Inc., Australia). DXA is the gold standard approach for measuring body composition, but is expensive and not always available outside of a clinical setting. BIA has been recommended as a technique to measure sarcopenia in the elderly [51] and is as accurate and reliable [52, 53] yet more practical than other types of body composition techniques such as DXA or skinfolds because it is portable and does not rely on extensive technician training and experience [54]. If we can show equal classification and sensitivity to change with BIA we can use this measurement technique instead of DXA in future implementation trials. Cutoffs for sarcopenia have been established. We will use a cutoff score for moderate sarcopenia in men of  $\leq 10.75 \text{ kg/m}^2$  based measures from men aged 60+ in the NHANES II database [55]. Since obese, rather than traditionally defined frailty is an emerging concept and our data suggest obese frailty increases risk for falls even more than traditional frailty, we will calculate obesity frailty by substituting  $\text{BMI} > 30 \text{ kg/m}^2$  for SMI and repeating analyses. We will also record weight on a scale at each visit.

2. *Exhaustion*: We will use the self-reported score on SF-36 Vitality Scale which we have used to characterize exhaustion for frailty in cancer survivors [56] and which has established reliability [57], has been validated in cancer survivors as a fatigue measure[58] and has shown sensitivity to change in response to exercise in adult, older adult and clinical populations, including cancer [59-61]. We will use cutpoints of scores of less than 50.00 (normed) for prostate cancer survivors aged 50-64 years or scores less than 40.00 (normed) for prostate cancer survivors aged 65+ years. Cutpoints are lowest quartile of scale in general U.S. population [57]. The Functional Assessment of Chronic Illness Therapy (FACIT) Fatigue scale will also be administered. It is a 13-item questionnaire. Though not used in frailty assessment, but used to evaluate reductions in cancer-related fatigue from exercise [62], we can also consider changes in the fatigue subscale of the QLQC30 which could be more sensitive in prostate cancer survivors (see below).
3. *Low Activity*: Low activity will be measured by physical activity-related energy expenditure (METS), calculated from self-report physical activity. We will use Fried's original cutpoints for "low activity": <383 kcals per week spent in moderate-vigorous intensity activity measured by the 41-item Community Healthy Activities Model Program for Seniors (CHAMPS) physical activity questionnaire. [63] CHAMPS is a common and highly reliable [64] measure of physical activity in older adults, including our studies in cancer survivors [33, 49, 65, 66]. We considered using accelerometry to track activity levels but this technique introduces considerable expense and personnel resources. Given our available resources we will be able to conduct a sub-study on 2 study waves (~100 men) to compare objective to self-report methods for tracking activity change over time.
4. *Slowness*: Walking speed will be measured as the fastest time of two 15' walks at a usual pace. Walks will be performed on an electronic gait mat to ensure accurate timing. We will use Fried's original cutpoints for "slowness" in older men of time  $\geq 7$  seconds for height  $\geq 173$  cm or time  $\geq 6$  seconds for height  $< 173$  cm. Test-retest correlations for average walk speed are strong: 0.72-0.93[67]. 3 meter Timed Up and Go will also be collected as a measure of slowness.
5. *Weakness*: In contrast to grip strength used by Fried in her original phenotype, lower body strength is more closely linked to falls, mobility, and dysfunction and can be easily obtained using well established timed chair stand test (seconds required to rise from chair 5 times)[68, 69]. Chair stand time  $\geq 12$  seconds has been shown to predict a 2.4 increased risk of falls in older adults and we will apply this cutoff for "weakness"[70].

We will also assess frailty at baseline using the FRAIL scale self-report measure, as we have done in our previous study [8].

Secondary Endpoint: Physical Function: Physical function will be measured objectively (mobility, balance) and subjectively (perceived function by self-report).

*Functional Mobility*: The Timed Up and Go (TUG) test is a reliable [71] and widely accepted clinical measure of mobility that evaluates the time that it takes a person to rise from a chair, walk 7 m, turn around a cone and return and sit in the chair [72]. Slower TUG times are associated with an increased risk of falls [73] and disability [69]. [name], a Co-Investigator, developed an instrumented version of the TUG test that incorporates wearable sensors to detect changes in mobility that are not apparent from the stopwatch TUG score.[74] The iTUG system can electronically capture individual elements of the TUG test at a very sensitive level to detect small changes over time and decrements in higher functioning patients that might be missed by a stopwatch time. TUG time is our main outcome, but we will examine additional information provided by the iTUG (e.g., segment time, step #) to understand which components of mobility ADT affects. A 7-meter dual task will also be conducted. A participant will be asked to count

backwards by 3's starting at 99. In addition, standing balance tests will be done as part of the Physical Performance Battery.

**Functional Balance:** Postural sway is a reliable [75] measure of how well a person can maintain their equilibrium during quiet standing. Increased sway indicates poor balance control and is associated with falls [72]. We will conduct two standard 30-second postural sway test to measure the sway area ( $m^2/s^3$ ) and amount ( $m/s^2$ ) and velocity (m/s) of sway during quiet standing with feet together and eyes closed and feet together eyes open using lightweight, inertial wireless sensors worn on the trunk [75]. Lateral sway velocity is the outcome of interest because it is a strong predictor of falls in older adults[76] and may detect changes in balance associated with cancer treatment [77].

**Passive monitoring of functional mobility and balance:** Because people can perform better in a testing environment than how they normally move in daily life [78], we will also collect gait and balance measures using SmartSox passive monitoring sensors. SmartSox are a new product developed by APDM, Inc, that also manufactures the iTUG and postural sway sensors used in this study. SmartSox are a thin neoprene wrap that is worn under socks throughout the day and provides continuous passive monitoring of gait and balance. In addition to the postural sway measurements listed above, we will ask participants to wear SmartSox sensors for 8-10 hours daily for up to 7 days per measurement period. Data are transmitted the same way as data from the iTUG and postural sway sensors and participants charge the socks each night just like a smart phone. SmartSox passively collect gait and balance measures such as quality and quantity of walking activity. These metrics may be more sensitive indicators of mobility problems since they can detect decrements in gait and balance that are not picked up by traditional timed tests in the clinic or gait laboratory. Participants will document SmartSox use in a daily diary (i.e., date, time put on and taken off each day).

**Perceived Physical Function** will be measured by self-report using the physical function subscale of the European Organization for Research and Treatment of Cancer Quality of Life Questionnaire (EORTC QLQ-C30; version 3, App. I), a cancer-specific measure and common in studies of prostate cancer survivors, including ours [37, 79].

Flexibility may improve in the control group, so we will measure flexibility in all groups using the standardized Chair Sit and Reach Test for lower body flexibility. This test is designed for and validated in older adults. Lower scores indicate more flexibility.

Study visits may be delivered in-person with additional precautions and/or delivered remotely via video conferencing. In order to determine the validity of remote delivery, participants may be asked to complete both sets of testing at every time point (in-person plus remote). In such cases remuneration will be offered to offset the additional time asked of participants. If delivered remotely, select testing measures will be adapted to this type of delivery. These testing measures include:

1. Height
2. Weight
3. Flexibility (chair sit and reach, see Secondary Endpoint: Physical Function, above)
4. Physical Performance Battery (PPB) (see Secondary Endpoint: Physical Function, above)
5. Passive monitoring of functional mobility and balance (see Secondary Endpoint: Physical Function, above)
6. 3m TUG (see Secondary Endpoint 4. Slowness, above)
7. All surveys (see Primary Endpoints and Secondary Endpoints, above) will continue to be sent out electronically as previously described. If a participant needs a paper survey to complete the survey, one will be provided or their data will be marked as "missed" if study

staff are unable to mail a paper survey to the participant during their outlined testing window.

The following measures will not be collected remotely:

1. DXA scan and BIA (see Secondary Endpoint 1. Shrinking, above)
2. Functional Mobility and Functional Balance (see Secondary Endpoint, above)

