### **3.0 STUDY DESIGN/METHODOLOGY**

To address study aims we propose the GET FIT Prostate trial (Group Exercise Training for Fall prevention and functional Improvements during and after Treatment for Prostate cancer) - a single-blind, parallel group, randomized controlled trial comparing- 1) tai ji quan and 2) strength training against each other and vs. 3) a placebo control - over a 6-mos. supervised intervention (Aims 1 & 2) and 6-mos. follow-up (Aim 3).

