Interested participants will be screened either by phone or in person using an IRB approved screening script. After initial screening, potentially eligible men will be scheduled for consent and baseline screening and possible further baseline testing in qualified men. Screening includes review of fall history in the past year, a 3-meter Timed Up and Go walk at usual pace, and standing up and down from a chair five times as fast as safely possible. The testing session will include DXA, performance testing and survey completion and will be repeated at 3- and 6-mos. (post-intervention), and 6 mos. after completion of the intervention (follow-up). Total time for performance testing and survey completion is ~2-2.5 hours. Men will complete written surveys on a computer at baseline and online for follow-up visits, unless they prefer to complete paper surveys. Staff will review surveys for completeness and follow up with participants in person or by phone on missing data. To reduce bias we will retain blinding of the research assistants who conduct the testing visits, by having the Project Director provide each participant with an envelope that contains his random group assignment *after* baseline testing is complete. Qualified men will

be randomly assigned to 1 of 3 groups: 1) tai ji quan, 2) strength training or 3) stretching control. To avoid confounding and differential tolerance to exercise by ADT history and age, block randomization stratifying for timing of ADT (past or current) and will be done using EXCEL to generate random assignments from each block. Assignment will be in random blocks of 6 to 9 within each wave (~42-48 men) to facilitate even enrollment and to prevent the Project Director from predicting group assignment.

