#### **SCHEDULE OF EVENTS**

Procedures	Eligibility Screening	Baseline Testing	Intervention (Month 1-6)	Post-Intervention (Month 7-12)	3-Month Testing	6-Month Testing	9-Month Testing	12-Month Testing
Pre-screening eligibility	X							
Consent form	X							
Demographics – demographic questionnaire		X						

Procedures	Eligibility Screening	Baseline Testing	Intervention (Month 1-6)	Post-Intervention (Month 7-12)	3-Month Testing	6-Month Testing	9-Month Testing	12-Month Testing
Health history questionnaire		X			X	X		X
Comorbidities – FCI		X			X	X		X
Charlson Comorbidity Index		X						X
Disability - LLFDI		X			X	X		X
Fear of falling - SAFFE		X			X	X		X
Brief Pain Inventory		X			X	X		X
PROMIS Anxiety Short Form		X			X	X		X
Depression: CES-D		X			X	X		X
Vertigo		X			X	X		X
FACT-Cog		X			X	X		X
Cancer Loneliness Scale		X			X	X		X
Falls + AEs-Monthly			X	X				
Falls-Quarterly					X	X	X	X
Falls-Past year	X	X						
Exercise follow-up							X	X
FRAILTY								
Shrinking-BIA, DXA		X			X	X		X
Exhaustion-SF-36 Vitality Scale		X			X	X		X
FACIT-Fatigue		X			X	X		X
Low Activity-CHAMPS		X			X	X		X
Slowness-15' usual pace walk		X			X	X		X
Slowness- 3 meter TUG	X	X			X	X		X
Weakness-Chair stand test	X	X			X	X		X
FRAIL scale		X						
PHYSICAL FUNCTION								
Flexibility		X			X	X		X
Functional Mobility-7 meter TUG and dual task 7-meter TUG		X			X	X		X
Functional Balance-Postural sway, PPB standing balance		X			X	X		X
Physical functioning-6-minute walk		X			X	X		X
Passive monitoring of functional mobility and balance (SmartSox)		X				X		
Perceived Physical Function-EORTC QLQ-C30		X			X	X		X

Ancillary study:

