In this study we do not anticipate moderate or serious adverse events. Only moderate and serious adverse events that are related or possibly related to exercise sessions (i.e., group exercise classes, prescribed home program exercise, and physical performance measurement appointments) will be reported on our Adverse Events Log.

A survey (Adverse Events Survey) was created by the study team to be administered monthly during the participants' year long participation in the study. Adverse events reported through this survey may be followed-up by study staff with a phone call, e-mail, or in person in class during the intervention period, when participants self-report that their reporting condition is due to a study-related exercise activity or if more information is needed to determine reportability. Participants will also have the opportunity to report adverse events during exercise class or at physical performance measurement appointments.

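### The stated blind does not reach the step that decides whether a reported fall counts, and Aim 1 has no analysis that would show unequal rejection by arm

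*Combined protocol and SAP*

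**What the plan says.** Section 3.0 describes the trial as "a single-blind, parallel group, randomized controlled trial comparing" tai ji quan, strength training and a stretching control. The only statement of who is blinded is in Section 8.0, Screening tests and procedures: "To reduce bias we will retain blinding of the research assistants who conduct the testing visits". In the same place the Project Director is to "provide each participant with an envelope that contains his random group assignment" once baseline testing is done, so the men know their arm.

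Section 3.0, Primary Endpoint: Falls, takes the endpoint from the men's own monthly reports: "Participants will be provided with a monthly falls calendar to record falls when they occur". A recorded fall is then checked: "Each participant that records a fall will be phoned to confirm that each fall meets the standard definition", and the purpose is given as "in order to reduce the risk of false positives, and to obtain information about the fall (e.g., how it occurred) and any resultant injury". The definition leaves out falls caused by a major intrinsic event (stroke and syncope are the examples) or by an overwhelming hazard.

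The Schedule of Events in Section 8.0 puts two monthly collections in one row, "Falls + AEs-Monthly". Section 19.1 says that adverse events from the monthly survey "may be followed-up by study staff with a phone call, e-mail, or in person in class during the intervention period". The triggers are that the man himself attributes the condition to study exercise, or that more is needed to decide reportability.

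Section 13.0, Aim 1, fits a negative binomial model to each man's total falls from baseline to 6 months. The one further falls analysis named there concerns men who drop out.

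**The concern.** The protocol blinds its testing-visit assistants in order to reduce bias, so it accepts that knowing the arm can affect assessment. The primary endpoint does not pass through those visits. It is reported by unblinded men and then kept or removed after a phone call for which no blinding is stated.

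If qualifying falls were rejected more readily in one arm than another, the difference would go straight into the IRR that tests the primary hypothesis. It would also affect the tai ji quan versus strength training comparison. With one analysed count and no record of rejections by arm, nothing in the plan would show that it had happened.

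**Working it through.** **Which steps are covered by the blind**

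- Stated as blinded: research assistants at testing visits (Section 8.0).
- Known to be unblinded: the men, who are given their assignment and attend visibly different classes.
- Not stated anywhere: who makes the confirmation call, who decides that a fall qualifies, whether either is blinded, whether a script is used, and how rejected falls are logged.

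The call goes only to men who record a fall. As described, it can remove falls but does not look for missed ones.

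**Whether the arm could become known**

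The caller asks how the fall occurred. Section 3.0 gives the arms different opportunities for a fall in class: weighted-vest lunges and step-ups in strength training, balance-challenging forms in tai ji quan, and stretching done sitting or lying down. A man describing a fall in class could therefore reveal his arm. Adverse-event follow-up could do so too.

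**Size of a possible bias**

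Inputs from Section 13.0: target IRR 1 − 0.47 = 0.53; 100 evaluable men per group; alpha 0.05 (taken as two-sided, since the plan does not say); overdispersion 2.5. Confirmation rates and the control fall rate over six months are not given, so both are assumed. The plan has no confirmation figure to reproduce. Its sample size is not in dispute here, and it cannot be reproduced without a control fall rate.

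Let c_E and c_C be the shares of qualifying reported falls kept in an exercise arm and in control. Then

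expected IRR = true IRR × c_E / c_C.

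| Kept: exercise vs control | Ratio | True 1.00 becomes | True 0.53 becomes |
|---|---|---|---|
| 90% vs 95% | 0.90/0.95 = 0.947 | 0.95 | 0.50 |
| 85% vs 95% | 0.85/0.95 = 0.895 | 0.89 | 0.47 |
| 80% vs 90% | 0.80/0.90 = 0.889 | 0.89 | 0.47 |
| 70% vs 90% | 0.70/0.90 = 0.778 | 0.78 | 0.41 |
| 95% vs 85% | 0.95/0.85 = 1.118 | 1.12 | 0.59 |
| equal | 1 | 1.00 | 0.53 |

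The direction is also an assumption. The fifth row shows the bias running against the exercise arms.

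**Effect on the false-positive rate**

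Take a true IRR of 1, m falls per man over six months, m_C = c_C·m, m_E = c_E·m and d = ln(m_E/m_C). With 100 men per arm:

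- 2.5 read as a variance multiplier: SE² = 2.5(1/m_C + 1/m_E)/100.
- 2.5 read as the negative binomial dispersion: SE² = (1/m_C + 1/m_E + 2 × 2.5)/100.
- Rejection probability = Φ(−1.96 − d/SE) + Φ(−1.96 + d/SE).

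Example with m = 1.0 and 85% vs 95% kept: m_C = 0.95, m_E = 0.85 and d = −0.111. Under the first reading SE = √(2.5 × (1.053 + 1.176)/100) = 0.236. The probability is 0.068 + 0.008 = 0.076.

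Over m from 0.3 to 1.2 and both readings of 2.5:

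| Kept: exercise vs control | False-positive rate (nominal 5%) |
|---|---|
| 95% vs 100% | 5.2% to 5.7% |
| 85% vs 95% | 5.8% to 8.1% |
| 80% vs 90% | 5.8% to 8.3% |
| 70% vs 90% | 8.5% to 19.4% |

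**The case against.** A reader might infer three stronger things, and the documents support none of them.

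- *That the caller is unblinded.* The protocol is silent on this. The blinded research assistants could be the callers.
- *That the confirmation call is part of adverse-event follow-up.* The shared row in the Schedule of Events shows joint monthly collection only. No text makes the two one contact or gives them one caller, and follow-up of adverse events is discretionary.
- *That adverse-event follow-up discloses the arm.* In Section 19.1, attribution to study exercise is the man's own report and a trigger for contact. It is not a described question. All three arms attend supervised classes of equal length, so the attribution alone does not identify the arm.

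Other points also have weight. The intrinsic-event exclusion is narrow, with named examples, although overwhelming hazard is looser. The same definition and call apply in every arm, and nothing shows how often falls would be rejected. Small differences in rejection do little harm. The quarterly falls questionnaire, for which no confirmation call is described, is a possible cross-check; but Aim 1 does not use it and no rule reconciles it with the monthly reports. Finally, men in an exercise trial cannot be blinded, and masking the decision does not change what they choose to report.

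What is left after these points is the gap itself: the step that settles the primary count has no stated protection from knowledge of the arm and no planned check.

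**Conclusion.** The point holds as an unprotected step with a cheap improvement. It is not a demonstrated failure of the blind, because unequal rejection is a possibility and not a documented event.

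If rejection of qualifying falls differed by 5 to 10 percentage points from a 95% confirmation rate in control, the IRR would shift by about 5% to 11%. At the 10-point difference the false-positive rate would be roughly 6–8%. A 20-point difference from 90% would be serious.

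These sizes rest on assumed confirmation rates, an assumed direction, an assumed control fall rate, and the removal of falls that truly met the definition. If one arm simply had more non-qualifying events, removing them would be correct and not a bias. Equal rejection leaves the expected IRR unchanged.

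**What to change.** 1. **Section 3.0, Primary Endpoint: Falls.** State that whether a reported fall meets the definition is decided by existing blinded staff, for example the testing-visit research assistants. They should work from a scripted description with class and exercise type left out, separately from adverse-event follow-up. Having them read the description instead of making the call also protects their blind at testing visits.
2. **Section 13.0, Aim 1.** Pre-specify a sensitivity analysis: the same negative binomial model on all self-reported falls before confirmation. It includes non-qualifying falls, so a different IRR is a prompt to examine the rejections and not proof of bias.
3. **Reporting.** Add a table of reported, confirmed and rejected falls, with reasons, by arm.
4. **Falls already handled.** Re-judge them only if call notes were retained. Ancillary study #2 already cites baseline data on 284 men, so a change to the call may come late for many. The sensitivity model and table remain possible if the monthly reports were kept as returned.

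The cost is a little extra workflow to mask short descriptions and keep the two follow-ups apart, plus one model and one table. Reporting bias from men who know their arm remains and should be acknowledged as a limitation.
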